Study design and plan	This is an open-label, randomized Phase II study in patients with unresectable esophageal cancer
Planned number of patients	Total number of patients: 72-78 patients
	Number of patients per center: 9-15
	Number of patients per treatment arm: 33-36 patients

Schedule of visits and assessments**Within 4 weeks prior to treatment start**

- Written informed consent
- Medical History
- Clinical staging (endoscopy incl. biopsy)
- Endoscopic ultrasound
- Tumor Assessment CT/MRI chest and abdomen
- ECG and LVEF
- FEV₁
- Evaluation by a surgeon with respect to resectability
- Tissue immunohistochemistry

Within 7 days prior to treatment start

- Height, weight, vital signs
- Karnofsky-Performance Status
- Hematology (leucocytes, neutrophils, platelets, erythrocytes, hemoglobin)
- Clinical Chemistry (sodium, potassium, calcium, magnesium, creatinine, bilirubin, SGOT, SGPT, LDH, alkaline phosphatase, γ -GT)
- Pregnancy test in women of child-bearing potential
- Serum sample (10 ml) and whole blood sample (10 ml) for EGFR and ligands determination (if patient agrees to participate in translational study)

Evaluations during radio-immunochemotherapy:**Weekly:**

- Vital signs
- Weight
- Hematology (leucocytes, neutrophils, platelets, erythrocytes, hemoglobin)
- Clinical signs and symptoms, toxicity according to the NCI-CTC version 4.0
- DC-MRT: at day 7 (+/-2) or day 14 (+/-2) of the first cycle (in selected centers)

Every 4 weeks:

- Karnofsky-Performance Status
- Biochemistry (sodium, potassium, calcium, magnesium, creatinine, bilirubin, SGOT, SGPT, LDH, alkaline phosphatase, γ -GT)

After 4-4.5 weeks (36-41.4 Gy):

- Endoscopy (incl. biopsy, if patient agrees to participate in translational study)
- Endoscopic ultrasound (optional)
- Tumor assessment (CT/MRI chest and abdomen)
- serum sample (10 ml) for EGFR and ligands determination (if patient agrees to participate in translational study)

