8.3 Statistical analysis

8.3.1 Statistical Methode

Treatment outcome:

Loco-regional control is defined as absence of loco-regional progression based on findings of endoscopy, endoscopic ultrasound, and computed tomography.

OS, PFS, MFS and LC are calculated for both treatment groups and for several potential prognostic factors with the Kaplan-Meier method and measured from the day of randomization .

Such potential prognostic factors are: age (≤ 60 vs. > 60 years), Karnofsky performance status (100%-80% vs. 70%), tumor location (upper third vs. middle third vs. lower third), tumor length (< 7 cm vs. ≥ 7 cm, according to endoscopy), histology (squamous cell carcinoma vs. adenocarcinoma), histologic grade (G1-2 vs. G3), T-stage (T2-3 vs. T4, according to endoscopic ultrasound and computed tomography), N-Stage (N0 vs. N+), and hemoglobin before radiotherapy (< 12 vs. 12-14 vs. > 14 g/dl).

Differences between the Kaplan-Meier curves are evaluated with the log-rank test. Results are considered significant if $P < 0.05$. Potential prognostic factors found to be significant in the univariate analysis, are evaluated in a multivariate analysis performed with the Cox proportional hazard model.

Stratification at randomization according to :

Histology (SCC vs. adeno)

KPS (100%-80% vs. 70%)

Stage (T1-3 N0-1 vs. T4 and/or N2 and/or M1a)

Toxicity:

Both treatment groups are compared for toxicity using the Chi-square test.

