8.4 Sample size calculation

This phase II study is an explorative randomized study with 2 parallel groups. Using a standard single-stage phase II design by FLEMING (1981), $n = 62$ patients evaluable for efficacy have to be recruited. As a similar number of patients is to be recruited to the standard arm, a total number of 124 patients is required. The standard treatment control group serves to reduce some of the result variability which is typically encountered in single-arm phase II trials, especially caused by patient selection phenomena and investigator bias. To cover potentially drop outs 67 patients per arm will be recruited.

The OS rate after 2 years is chosen as primary efficacy endpoint. The estimation of the efficacy rate of 40% of the reference group is based on the findings of several studies [49-54]. Therefore, the respective experimental therapy arm would be rated as insufficiently active, if the observed OS rate at 2 years is 40 % or lower.

On the other hand, the experimental therapy would be considered to be a very promising candidate for further development (e.g. in a phase III trial), if the true OS rate at 2 years amounted to 45 % or more.

Probability to accept the experimental therapy as promising ($> 45\%$ OS rate) with respect to efficacy, in spite of a true OS rate of $\leq 40\%$: 5% (type I error).

Probability to reject the experimental therapy as not sufficiently efficient ($\leq 40\%$), although the true OS rate is promising ($> 45\%$): 20% (type II error, corresponding to a power of 80%).

However, the last patient will be randomized on December 31, 2016 at the latest, which is 2.5 years later than originally planned. Based on number of patients randomized until end of July and who received study treatment ($n=66$) it is expected that the total number of patients in the Full Analysis Set (FAS) will be between 72 and 78 patients, while the number of patients in the Per Protocol Population is expected to be between 66 and 72 patients.

The final conclusion of the phase II trial will depend on the definite OS rate (and its confidence interval), the respective findings in the 5-FU/cisplatin reference arm, as well as the information on type, frequency and severity of toxicities.

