The 2-years overall survival rates will be estimated using Kaplan-Meier methods and the difference between treatment groups regarding 2-years overall survival curves will be compared using the log-rank test. In addition, univariate Cox proportional hazard methods will be used to estimate the corresponding hazard ratio (HR) and 95% confidence intervals for HR.

Based on the expected number of patients randomized until end of 2016, the following difference (hazard ratios) can be detected between the two treatment arms with 80% power and a two-sided significance level of 0.05, assuming that the 2-years OS probability is between 30 and 40%, and number of lost-to-follow-ups is about 5% during the 2 years.

Table 10: Hazard ratios and necessary numbers of events

Sample size	2-year OS probability		Necessary number of events	Hazard ratio
	CT only	CT plus Cetuximab		
2 x 33	30%	63.14	34	0.3820
	35%	68.38	31	0.3621
	40%	73.19	28	0.3407
2 x 36	30%	61.73	38	0.4007
	35%	67.02	35	0.3812
	40%	71.90	31	0.3601
2 x 39	30%	60.48	42	0.4177
	35%	65.81	38	0.3986
	40%	70.74	34	0.3778

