A separate DSMB charter will be set up which defines the roles and responsibilities of the DSMB, delineates qualifications of the membership, describes the purpose and timing of meetings, provides the procedures for ensuring confidentiality and proper communication, and outlines the content of the reports. In addition, the statistical guidance for evaluating safety and their associated stopping rules will be presented. These rules are meant as guidance rather than as mandatory decision rule. In case of unexpected results, the DSMB has the discretion to deviate appropriately from this guidance.

In case of significant excess toxicity associated with the experimental arm, the DSMB may decide together with the sponsor to stop the trial early due to safety concerns.

11 Ethical and regulatory aspects

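### The only planned between-arm toxicity analysis is a chi-square test, with no risk difference or confidence interval, so at 36–39 patients per arm a non-significant result could be misread as no excess toxicity

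*Combined protocol and SAP*

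**What the plan says.** Section 8.3.1 covers the arm comparison for toxicity in one sentence, repeated in the synopsis under statistical methods: "Both treatment groups are compared for toxicity using the Chi-square test". It names no toxicity endpoint, effect measure, interval or tolerable excess. A 5% significance threshold does appear in 8.3.1, but in the treatment-outcome paragraph, directly after "Differences between the Kaplan-Meier curves are evaluated with the log-rank test". It is not repeated under toxicity.

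Section 8.4 makes the final conclusion depend on the OS rate with its confidence interval, the reference-arm findings, "as well as the information on type, frequency and severity of toxicities". It also plans 95% confidence intervals for the hazard ratio.

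On size, section 8.4 says "it is expected that the total number of patients in the Full Analysis Set (FAS) will be between 72 and 78 patients". The synopsis has "Number of patients per treatment arm: 33-36 patients". Section 8.1 assigns safety analyses to the Safety Analysis Set, whose size is not projected.

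**The concern.** Section 2.4 makes the feasibility of adding cetuximab an aim of the study. Section 8.3.3 justifies the trial by the need for a first indication of the balance of benefit and risk, and allows direct expansion into phase III. That judgement needs the size of any toxicity excess and its uncertainty. A chi-square test supplies neither: it only separates significant from non-significant differences, and in a trial this small the second outcome is common even when the true excess is large.

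The plan asks for intervals on the efficacy side and not on the safety side. A final report that follows it literally could set a survival estimate with its interval beside a toxicity P-value without one. A reader could then take a non-significant P-value to mean that there is no excess.

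**Working it through.** **Inputs from the documents.** Chi-square test (8.3.1). Full Analysis Set of 72–78 (8.4) in two similar arms: 72/2 = 36 and 78/2 = 39 per arm, used as a proxy for the Safety Analysis Set. Two-sided 5%, borrowed from the OS calculation in 8.4 ("with 80% power and a two-sided significance level of 0.05"), because no level is attached to the toxicity test.

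**Assumed inputs.** The documents give no expected severe-toxicity rate for the control arm. I vary it from 10% to 70% and set the excess at 20 points.

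**Step 1: the plan's own figure.** There is no power figure for toxicity. The nearest is Table 10 for OS. With HR = ln(S_exp)/ln(S_ctrl) and events = 4 × (1.960 + 0.842)² / (ln HR)², the row for 2 × 36 with 40% in the control arm gives HR = ln(0.7190)/ln(0.40) = 0.360 and 31.4/1.044 = 30.1, so 31 events, as stated. Eight of the nine rows match exactly; the ninth (2 × 36, 35%) gives 34 against a stated 35. So the two-sided 5% level and equal arms are the plan's own working assumptions at these sizes.

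**Step 2: chance of missing a 20-point excess.** Over all pairs of binomial counts, the uncorrected Pearson statistic rejects above 3.841. The miss rate is 1 minus the summed probability of rejection.

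| Control vs cetuximab | 36 per arm | 39 per arm |
|---|---|---|
| 10% vs 30% | 42.1% | 38.0% |
| 20% vs 40% | 52.9% | 49.7% |
| 30% vs 50% | 59.0% | 55.6% |
| 40% vs 60% | 61.7% | 56.1% |
| 50% vs 70% | 59.0% | 55.6% |
| 60% vs 80% | 52.9% | 49.7% |
| 70% vs 90% | 42.1% | 38.0% |

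Normal-approximation check for 40% vs 60% at 36 per arm: z = (0.20 − 1.96 × √(2 × 0.5 × 0.5/36)) / √((0.24 + 0.24)/36) = (0.200 − 0.231)/0.1155 = −0.27, a miss rate of 60.6%.

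**Step 3: sensitivity, control rates 20–60%.** At 33 per arm, the low end in the synopsis, the miss rate is 56–59%. With Yates correction at 36–39 per arm it is 61–71%. At the 67 per arm set for recruitment in 8.4 it would be 28–37%. For 80% power against a 20-point excess, 82–97 per arm are needed at control rates of 30–60%, and 62 at 10% or 70%.

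**Step 4: what an interval would show.** Take 18/36 in both arms. The Wilson limits are 0.345 and 0.655, so the Newcombe 95% limits for the difference are ±√(0.155² + 0.155²) = ±0.22. The simple Wald half-width is 1.96 × √(2 × 0.25/36) = 0.231, or 0.222 at 39 per arm. An observed difference of zero thus leaves an upper limit of about 22 points. At the unfavourable edge of non-significance, 22/36 vs 14/36 gives a chi-square of 3.56 and a Newcombe interval of −1 to +42 points.

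**The case against.** The strongest reply is that this is an explorative phase II trial whose plan disclaims a rigorous comparison of arms (8.3.3), and that section 8.4 weighs the kind, frequency and grade of toxicities without mentioning a P-value. A chi-square table already contains the counts by arm, so anyone can read off the difference. Much of this stands, and it rules out several stronger readings that a reader might infer:

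- *Toxicity is judged by the test alone.* Section 8.4 does not say so. The test is the only planned between-arm analysis, which is a narrower statement.
- *Toxicity is tested at P < 0.05.* The threshold sits with the log-rank test. Applying it to toxicity is reasonable, but it is not explicit.
- *A non-significant result will be accepted as proof of safety.* No passage sets such a rule. The risk is one of misreading.
- *The stopping provision in section 10 demands a significant test.* It reads "In case of significant excess toxicity associated with the experimental arm, the DSMB may decide together with the sponsor to stop the trial early", but names no test or level. The statistical guidance is left to a charter, is described as guidance only, and leaves the board discretion. Nothing here calls for rewording it.
- *Non-significance always leaves more than 30 points open.* That holds at the unfavourable edge (22/36 vs 14/36), not in general.

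The reply does not supply the missing interval. A difference read from counts carries no statement of its uncertainty. A design that disclaims formal comparison is better served by estimation than by a test alone. The charter is described as serving the board's reviews, and nothing extends it to the final comparison.

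**Conclusion.** The concern holds as a gap in the planned toxicity analysis: a test is named, and an effect estimate with its uncertainty is not. For a 20-point excess at 36–39 per arm, the two-sided 5% test misses about 50–62% of the time at control rates of 20–60%, and about 38–42% at 10% or 70%. Equal observed rates near 50% would leave an upper 95% limit of about 22 points.

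These figures rest on the assumed control rates, on the 5% level taken from elsewhere in the plan, on the uncorrected chi-square, and on the Full Analysis Set projection standing in for the Safety Analysis Set. The change is worth making because toxicity feeds the final conclusion. The documents do not support a claim that the trial would declare the regimen safe on a non-significant P-value.

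**What to change.** In section 8.3.1 and the synopsis, replace the toxicity sentence with wording to this effect: for each toxicity category, and for the incidence of patients with grade III/IV adverse events and of serious adverse events, the proportion affected is reported by arm with the risk difference (arm A minus arm B) and its 95% confidence interval (Newcombe or Miettinen–Nurminen); the chi-square P-value is descriptive; a non-significant test is not evidence of no excess toxicity.

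The cost is a wording change and an extra column in the toxicity tables, with no additional patients or data. The intervals do not add power: at this size they will usually be unable to exclude a 20-point excess when rates are mid-range. That is the downside for the sponsor, since the report must say openly that a sizeable excess remains possible.

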11.6	Notification to authorities	58
11.7	Sponsorship.....	58
12	Study management	59
12.1	Case Report Form handling	59
12.2	Source data and subject files	59
12.3	Investigator Site File and archiving.....	59
12.4	Monitoring, Quality Assurance and inspection by authorities.....	60
12.5	Changes to the study protocol.....	60
12.6	Study report and publication policy.....	61
13	References.....	62

APPENDICES

Appendix 1	Protocol Signature Pages
Appendix 2	Patient information sheet and consent form
Appendix 3	Karnofsky Performance Status Scale
Appendix 4	RECIST criteria (Version 1.1)
Appendix 5	Treatment of acneiform skin reactions related to Cetuximab
Appendix 6	Management options for radiation dermatitis and co-existing acneiform skin reactions related to Cetuximab
Appendix 7	NCI Common Toxicity Criteria Version 4.0
Appendix 8	Summary of product characteristics Cetuximab
Appendix 9	Summary of product characteristics 5-FU
Appendix 10	Summary of product characteristics Cisplatin

1 Synopsis

Study number	Definitive radiochemotherapy with 5-FU / cisplatin plus/minus cetuximab in unresectable locally advanced esophageal cancer: a phase II study
EudraCT number	2010-023427-18
Acronym	LEOPARD-II
Sponsor	University Hospital Schleswig-Holstein, Campus Luebeck, [name]
Principal investigator	[name], University Hospital Schleswig-Holstein, Campus Luebeck, Department of Radiation Oncology, [name]
Study phase	Phase II
Study center(s)/country(ies)	Approximately 15 German Centers
Planned study period (first enrollment-last subject out)	Start of Enrolment (FPI): Q3 / 2011
	End of Enrolment (LPI): Q4 / 2016
	End of Treatment period (LP off treatment): Q1 / 2017
	End of Follow-up period (LP off study): Q1 / 2019
Study objectives	Primary objective: 2-year overall survival (OS)
	Secondary objectives: 
 • 1-year OS • 1-year and 2-year progression-free survival (PFS) • 1-year and 2-year loco-regional control (LC) • 1-year and 2-year metastases-free survival (MFS) • Toxicity (NCI-CTC 4.0) • Overall response rate (RECIST Version 1.1) • Quality of Life (EORTC QLQ-C30 and QLQ OES18) 
In addition the following parameters will be assessed irrespective of a specific time point:
 
 • OS • PFS • MFS

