6.1 Adverse events

6.1.1 Definition of adverse event, adverse drug reaction and serious adverse event

6.1.1.1 Adverse events (or adverse experience) (AE)

An AE is any untoward medical occurrence in a patient or clinical investigation subject administered a pharmaceutical product and which does not necessarily have a causal relationship with this treatment.

An AE can therefore be any unfavorable and unintended sign (including an abnormal laboratory finding, for example), symptom, or disease temporally associated with the use of a medicinal product, whether or not considered related to the medicinal product.

Due to regulatory requirements, events occurring during pre- and post-treatment periods should also be designated as AEs. Therefore, safety surveillance - reporting of (S)AEs - commences at the time when the subject is enrolled into the study (date of signature of the informed consent) until the End of Study Visit has been performed. Therefore events occurring in the period between the signed informed consent and beginning of the study drug administration are to be designated as AEs. This procedure complies with requirements by some authorities.

6.1.1.2 Adverse drug reaction (ADR):

All noxious and unintended responses to a medicinal product related to any dose should be considered adverse drug reactions (ADRs).

The phrase "responses to a medicinal product" means that a causal relationship between a medicinal product and an AE is at least a reasonable possibility i.e. the relationship cannot be ruled out.

6.1.1.3 Serious adverse event or reaction/experience (SAE):

A serious AE (experience) or reaction is any untoward medical occurrence that at any dose:

- Results in death
- Is life-threatening

NOTE: The term "life-threatening" in the definition of "serious" refers to an event in which the subject was at risk of death at the time of the event; it does not refer to an event which hypothetically might have caused death if it were more severe.

- Requires in-patient hospitalization or prolongation of existing hospitalization
- Results in persistent or significant disability/incapacity
- Is a congenital anomaly/birth defect or
- Is an important medical event

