6.1.4 Monitoring of subjects with adverse events

Any AE that occurs in the course of a clinical study must be monitored and followed up until the End of Study Visit. Ongoing adverse events related to study treatment will be followed for 6 weeks (skin toxicities until outcome is known) after end of treatment. In addition SAEs must be reported via a SAE report form (see section 6.1.1.3 Procedure for reporting serious adverse events).

It is the responsibility of the investigator that any necessary additional therapeutic measures and follow-up procedures are performed.

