7.4 Evaluations during the Follow up phase

Follow-up assessments will terminate 2 years after the last patient has completed end of treatment (incl. biopsy, if patient agrees to participate in translational study).

- Evaluation of toxicity
- Treatment outcome
- Endoscopic ultrasound (optional)
Tumor Assessment (CT/MRI chest and abdomen)

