8.1 Analysis set descriptions

Safety Analysis Set

The safety population includes all patients who received at least one dose of trial medication and for whom at least one post-baseline safety measurement is available.

Full Analysis Set

The Full Analysis Set includes all patients who received at least one dose of trial medication and for whom at least one post-baseline efficacy measurement is available.

Per Protocol Set

This population includes all patients with at least six weeks of trial medication plus all patients who discontinued the study prematurely due to lack of efficacy, death or toxicity. Detailed criteria will be defined before analysis.

All safety analyses will be performed on the Safety Analysis Set. For efficacy analysis of the trial, the primary analyses will be based on the per-protocol set. Additional analyses will be performed on the Full Analysis Set for sensitivity purposes.

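### The chi-square comparison of toxicity has no time window, so for late toxicity it mixes the toxicity rate with survival; this is material only if the survival gap is large

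*Combined protocol and SAP*

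**What the plan says.** The whole toxicity analysis, in section 8.3.1 and again in the synopsis under statistical methods, is one sentence: "Both treatment groups are compared for toxicity using the Chi-square test". The denominator is the Safety Analysis Set (section 8.1): "The safety population includes all patients who received at least one dose of trial medication", with at least one later safety measurement. A treated patient who has such a measurement and then dies early therefore stays in the denominator.

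Collection runs well past the 14 weeks of treatment. Section 7.4 lists "Evaluation of toxicity" among the follow-up items, and the schedule of assessments puts these visits every 3 months. On duration, section 7.4 says: "Follow-up assessments will terminate 2 years after the last patient has completed end of treatment". Section 6.1.1.1 starts adverse event reporting at consent and continues it "until the End of Study Visit has been performed". The synopsis gives "Start of Enrolment (FPI): Q3 / 2011" and "End of Follow-up period (LP off study): Q1 / 2019".

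One sentence points the other way. Section 6.1.4, repeated in the synopsis, says: "Ongoing adverse events related to study treatment will be followed for 6 weeks (skin toxicities until outcome is known) after end of treatment". The sentence before it in section 6.1.4 follows every adverse event to the End of Study Visit.

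Neither place gives an analysis window, a split into acute and late events, a person-time rate, a time-to-event method for toxicity, or a rule for death.

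**The concern.** Late toxicity can be recorded only in a patient who is still alive and in follow-up. The trial looks for a survival difference. If there is one, the longer-living arm spends more time at risk, and its crude proportion with late toxicity rises for that reason alone. If cetuximab shortens survival, the same mechanism hides late toxicity in its arm.

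Section 8.4 makes the kind, frequency and severity of toxicity part of the final conclusion, beside the survival rate. A crude late-toxicity proportion could then be read as a higher toxicity rate under cetuximab when it partly reflects longer life.

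**Working it through.** **Inputs from the documents.** Patients per arm: 36 (synopsis, 33 to 36). Survival pairs at 2 years: 35% versus 67.02% (Table 10, 2 x 36), and 40% versus 45% (section 8.3.4). Shortest potential follow-up: 14/52 + 2 = 2.27 years. Longest: Q3 2011 to Q1 2019, about 7.5 years.

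**Assumptions, not in the documents.** Constant death hazard in each arm. The same late-toxicity hazard h in both arms while alive, 0.1 to 0.3 per year, counted from randomisation. The same follow-up T for every patient, 2.27 or 4 years.

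**The plan's own figure.** HR = ln(0.6702)/ln(0.35) = 0.4002/1.0498 = 0.3812, as in Table 10.

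**Step 1, death hazard.** m = -ln(S2)/2. For 35%, m = 0.5249 per year. For 67.02%, m = 0.2001.

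**Step 2, time at risk.** Person-years per patient = (1 - exp(-mT))/m.
- 35% versus 67.02%, T = 4: 1.672 versus 2.753, ratio 1.65. At T = 2.27: 1.326 versus 1.824, ratio 1.38.
- 40% versus 45%, T = 4: 1.833 versus 1.997, ratio 1.09.
- 35% versus 67.02% over 20 weeks (14 of treatment plus 6): 0.348 versus 0.370, ratio 1.06.

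**Step 3, crude proportion with late toxicity.** p = h/(m+h) x (1 - exp(-(m+h)T)). For h = 0.2 and T = 4, control: 0.2/0.7249 x (1 - exp(-2.900)) = 0.2759 x 0.9450 = 26.1%. Cetuximab: 0.2/0.4001 x (1 - exp(-1.600)) = 0.4999 x 0.7982 = 39.9%.

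**Step 4, rejection rate.** Exact binomial probability that the uncorrected chi-square is significant at two-sided 0.05 with more toxicity on cetuximab, 36 per arm. The nominal value in that direction is 2.5%.

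| 2-year OS | T (years) | h | Control | Cetuximab | Rejection |
|---|---|---|---|---|---|
| 35% vs 67.02% | 4 | 0.1 | 14.7% | 23.3% | 14.8% |
| | 4 | 0.2 | 26.1% | 39.9% | 24.7% |
| | 4 | 0.3 | 35.0% | 51.9% | 29.3% |
| | 2.27 | 0.1 | 12.1% | 16.5% | 7.8% |
| | 2.27 | 0.2 | 22.3% | 29.8% | 10.8% |
| | 2.27 | 0.3 | 30.8% | 40.7% | 14.4% |
| 40% vs 45% | 4 | 0.1 | 16.0% | 17.3% | 3.6% |
| | 4 | 0.2 | 28.2% | 30.3% | 4.0% |
| | 4 | 0.3 | 37.7% | 40.3% | 4.2% |

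**Step 5, any-toxicity endpoint.** If 80% in each arm already have an acute event (assumed), the proportion is 0.8 + 0.2p. At 35% versus 67.02% and T = 4 this gives 82.9% versus 84.7%, 85.2% versus 88.0%, and 87.0% versus 90.4%. Rejection is 4.0%, 5.6% and 7.1%.

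**Step 6, does the alternative remove it?** Events divided by toxicity-free person-years, h = 0.2, T = 4. Toxicity-free years per patient are p/h: 0.2607/0.2 = 1.304 and 0.3990/0.2 = 1.995. Control: 9.39 events/(36 x 1.304) = 0.20 per year. Cetuximab: 14.36/(36 x 1.995) = 0.20. The rate ratio is 1.00.

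**The case against.** The plan defines no late-toxicity endpoint and does not say that the chi-square pools every event to close-out. The only toxicity summaries it specifies are those for the safety board: the overall incidence of patients with any grade III/IV event, and serious events. After chemoradiation, acute events would be expected to dominate the first of these. This stands, and step 5 shows how far it shrinks the effect.

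The 35% versus 67.02% pair is a difference the reduced sample could detect, not the effect the plan expects. Its threshold for a promising result is 45%. This stands too. But the plan says 45% or more, and a trial of this size that shows a clear survival benefit will probably show a large observed gap.

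The synopsis and section 4.2.8 can be read as a fixed 2-year follow-up, although section 7.4 supports a common close-out. The 2.27-year rows cover that reading. A continuity correction, which the plan neither requires nor excludes, lowers the 4-year range from 15 to 29% to 9 to 21%.

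The 6-week sentence does not settle the matter. It concerns related events already ongoing at the end of treatment and does not end the collection of new ones.

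A reader might infer that the test would report a harm that does not exist. The documents do not support that. The crude excess is a true count of affected patients; it just cannot be read as a higher rate while alive. A reader might also blame the common close-out. It makes follow-up unequal between patients, but randomisation balances that between arms. The imbalance comes from death.

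**Conclusion.** The point holds in limited form. An unwindowed chi-square does not separate late toxicity from survival, and the plan names nothing else.

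The size depends on the survival gap and the endpoint. It is small at 40% versus 45%, and small for any-toxicity measures dominated by acute events. It matters only for late toxicity with a survival gap of Table 10 size. The 15 to 29% is not the error rate to expect from this trial: it needs that gap, 4 years of follow-up for everyone, a late-only endpoint and assumed hazards.

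The trial is exploratory, and toxicity is a secondary variable with no decision threshold attached. The importance is minor to moderate, and the case for changing the plan is that the change is cheap.

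**What to change.** In section 8.3.1 and the synopsis:

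- Keep the chi-square for acute toxicity, within a fixed window of the same length in both arms. This is an analysis window only and changes neither treatment nor data collection. Over 20 weeks the person-time ratio is at most about 1.06 in the cases above, so survival hardly affects it.
- For late grade 3 or higher toxicity, counted from the end of that window, compare the arms by the cause-specific hazard (log-rank or Cox, censored at death or last follow-up) or by person-time rates.
- Show crude proportions, or cumulative incidence with death as a competing event, as description only. With complete follow-up that cumulative incidence equals the crude proportion, so it does not remove the survival effect.
- Reconcile the 6-week and End of Study Visit sentences in section 6.1.4, and say which visit the latter is. The schedule of assessments has none of that name.

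The cost is some wording and one extra analysis. Onset dates are already recorded (section 6.1.2), and the survival analysis already needs dates of death or last contact (section 8.3.4).

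The downside is imprecision. At 36 per arm and the Table 10 gap, the 4-year proportions imply 5.3 + 8.4 = 13.7 late events (h = 0.1) to 12.6 + 18.7 = 31.3 (h = 0.3). The standard error of the log hazard ratio, about sqrt(1/d1 + 1/d2), is then 0.56 to 0.36. The 95% interval spans a factor of about 3.0 to 2.0 either side of the estimate. Also, a cause-specific hazard describes the rate among patients still alive, so it should be reported beside the survival result.
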